8 APPENDICES

8.1 Blinding Index Questionnaire

Version: For Subject to Complete

Sponsor and Protocol Number:

Subject Number: _____

Instructions: Now that you have completed this study, we want to ask your opinion about which treatment (real medication or placebo) you believe was administered to you in this clinical trial. Read all of the answer choices before circling your one answer to each question. There are no right or wrong answers. Your honest answers will be helpful for current and future research.

- 1. Which treatment do you believe you received? (CIRCLE ONE)
 - a. Strongly believe I received real medication
 - b. Somewhat believe I received real medication
 - c. Somewhat believe I received the placebo
 - d. Strongly believe I received the placebo
 - e. I don't know
- 2. If you answered "Don't know" above, please provide your best guess of the treatment you received in this clinical trial:

(CIRCLE ONE)

- a. I received the real medication
- b. I received placebo
- 3. In your own words, please describe the primary reason you believe you received this treatment?

This questionnaire was developed with primary reference from Bang H, Flaherty SP, Kolahi J, Park J. Blinding assessment in clinical trials: A review of statistical methods and a proposal of blinding assessment protocol. Clin Res Regul Aff. 2010;27:42-51.

Confidential

COR

8.2 Otoscopy Assessment of the Appearance of the Tympanic Membrane

Otoscopy will be performed by the physician investigator to assess the appearance of the TM in both ears regardless if AOM is bilateral or unilateral. Appearance of the TM will be evaluated for contour, color, fluid, and translucency as follows:

- Contour will be assessed using 1 of the following categories:
 - o Normal
 - Retracted
 - o Full
 - o Bulging
 - Perforated
 - Not assessable

The categorisation in normal/abnormal will be as follows:

- \circ Normal = normal
- Abnormal = retracted, full, bulging, or perforated
- Color will be assessed using 1 of the following categories:
 - o Normal
 - o Partly red
 - Completely red
 - Not assessable

The categorisation in normal/abnormal will be as follows:

- \circ Normal = normal
- Abnormal = partly red or completely red
- Fluid will be assessed using 1 of the following categories:
 - o No
 - Yes; if yes, color of fluid will be rated as yellow, translucent, red, blue, black, or not assessable.

The categorisation in normal/abnormal will be as follows:

- \circ Normal = no
- \circ Abnormal = yes
- Translucency will be assessed using 1 of the following categories
 - o Translucent
 - o Semi-opaque
 - o Opaque

• Not assessable

The categorisation in normal/abnormal will be as follows:

- \circ Normal = translucent
- Abnormal = semi-opaque or opaque

Satur

For appearance of the TM, 80% CIs will be calculated for the incidence of shifts from Baseline (0-60 minutes), from normal to abnormal for the right ear and, separately, for the left ear. If significance is found using 80% CIs, 90% and 95% CIs will also be tested. A table presenting all changes from Baseline (from/to normal from/to abnormal) will be summarised by treatment for all observed timepoints.

8.3 Device Experience Questionnaire-Study Staff Administering Treatment

For Clinical Staff

Thank you for completing the study activity. Please rate your agreement to the following statements and circle your response.

1. My first reaction to the study inhaler was positive.

	Strongly Disagree	Disagree	Neutral	Agree	Strongly Agree		
2.	The study inhaler Instructions for Use were clear and easy to follow.						
	Strongly Disagree	Disagree	Neutral	Agree	Strongly Agree		
3.	If I was not instructed	d, I feel confident tha	t I could have used th	e product witho	ut instruction.		
	Strongly Disagree	Disagree	Neutral	Agree	Strongly Agree		
4.	The study inhaler is e	easy to use.					
	Strongly Disagree	Disagree	Neutral	Agree	Strongly Agree		
5.	It was easy to place t	he study inhaler in th	e nostril.				
	Strongly Disagree	Disagree	Neutral	Agree	Strongly Agree		
6.	It was easy to press o	lown on the study inh	naler.				
	Strongly Disagree	Disagree	Neutral	Agree	Strongly Agree		
7.	Other comments.						
		ç					

Thank you, please hand the questionnaire back to the Principal Investigator.

Site No. Date

For Trial Subjects

Thank you for completing the study activity. Please rate your agreement to the following statements and circle your response.

1. My first reaction to the study inhaler was positive.

	Strongly Disagree	Disagree	Neutral	Agree	Strongly Agree						
Co	mments:				R						
2.	The study inhaler was comfortable in my nostril.										
	Strongly Disagree	Disagree	Neutral	Agree	Strongly Agree						
Co	mments:										
3.	3. The spray had a pleasant taste or aroma.										
	Strongly Disagree	Disagree	Neutral	Agree	Strongly Agree						
Comments:											
4.	4. There was no discomfort or irritation from the spray inside of the nose.										
	Strongly Disagree	Disagree	Neutral	Agree	Strongly Agree						
Co	mments:										
5.	Other comments	5.									
	9										

Thank you, please hand the questionnaire back to the Principal Investigator.

Subject No.	Site No.	Date

The purpose of this statistical analysis plan (SAP) is to outline the planned analyses and reporting to support the completion of the Clinical Study Report (CSR) for Novus Therapeutics Protocol OP0201-C-004. The planned analyses identified in this SAP will be included in regulatory submissions and/or future manuscripts. Also, exploratory analyses not necessarily identified in this SAP may be performed to support the clinical development program. Any posthoc, or unplanned, analyses not identified in this SAP will be clearly identified in the CSR.

The structure and content of this SAP provides sufficient detail to meet the requirements identified by the United States of America Food and Drug Administration and International Conference on Harmonisation (ICH) of Technical Requirements for Registration of Pharmaceuticals for Human Use: Guidance on Statistical Principles in Clinical Trials. All work planned and reported for this SAP will follow internationally accepted guidelines published by the American Statistical Association for statistical practice.

The following documents were also considered in preparation for writing this SAP:

- Clinical Research Protocol OP0201-C-004, Final, 10 Jul 2018, Administrative Change Number 1.0 Version 1.0, 15Nov2018
- ICH E3 Guideline: Structure and Content of Clinical Study Reports³
- ICH E6 Guideline on Good Clinical Practice⁴
- ICH E8 General Considerations for Clinical Trials⁵
- ICH E9 Statistical Principles for Clinical Trials⁶
- Statistical Analysis Plans: Principles and Practice⁷

The SAP is a supplement to the study protocol, which should be referred to for additional details on study design, study conduct, and other operational aspects of the study.

Confidential Page 8 of 33

1. BACKGROUND

Novus is developing OP0201 nasal aerosol ("OP0201"), a non-antibiotic and non-analgesic combination product intended to treat and prevent otitis media (OM). This study will evaluate the safety and immediate (within 60 minutes) reduction of ear pain caused by acute OM (AOM) in adults following a single intranasal dose of OP0201 20 mg.

2. STUDY OBJECTIVES

2.1 Primary Objective

The primary objective of the study is to assess the safety of intranasal OP0201 20 mg compared to placebo.

2.2 Exploratory Objectives

- To assess the effect of intranasal OP0201 20 mg compared to placebo on ear pain scores using the Visual Analog Scale (VAS)
- To assess the effect of intranasal OP0201 20 mg compared to placebo on ear pain scores using the Numeric Rating Scale (NRS-11)
- To assess impression of global change in symptoms as measured by Patient Global Impression of Change (PGIC)
- To assess impression of global change in symptoms as measured by the Clinical Global Impressions Scale: Global Improvement (CGI-I)
- To assess the effect of intranasal OP0201 20 mg compared to placebo on AOM symptoms
- To assess the blinding efforts as measured by the Blinding Index
- To evaluate Study Participant experience with the device as measured by the Device Experience, Questionnaire-Study Participant
- To evaluate study staff experience with the device as measured by the Device Experience Questionnaire-Study Staff Administering the Treatment

3. STUDY DESIGN

This is a single-dose, double-blind, placebo-controlled, randomized, parallel-group, proof-of-concept study to evaluate the safety and reduction of ear pain in adults with AOM. All study-related procedures, including screening, will be performed on Day 1. Assessment time points on Day 1 will be 10, 20, 30, and 60 minutes post dose. A safety follow-up call will occur on Day 7. The Schedule of Assessments is in Appendix A.

4. TREATMENT GROUPS AND STUDY ENDPOINTS

4.1 Treatment Group Comparisons

The treatment groups to be compared are OP0201 and placebo.

Confidential Page 9 of 33

4.2 Study Endpoints

4.2.1 Primary Endpoints

Primary endpoints are related to safety:

- Incidence, seriousness, severity, and relatedness to study treatment of adverse events (AEs) recorded over 60 minutes post dose and at Day 7
- Change from Baseline in vital signs (oral temperature, respiratory rate, pulse, blood pressure) at 60 minutes post dose
- Change from Baseline in ear, nose, and throat (ENT) examination (otoscopy of the ear, nose, and oropharynx) findings at 60 minutes post dose
- Change from Baseline in the appearance of the tympanic membrane (TM) (contour, color, fluid, translucency) as measured by otoscopy at 60 minutes post dose

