Study Drugs:	OP0201 is a drug-device combination product for intranasal metered dose inhaler delivery. The dry powder active ingredients (DPPC + CP) are suspended in propellant (HFA-134a). Each metered spray delivers 2.5 mg of OP0201 (20:1 ratio DPPC and CP, respectively) in 0.1 mL of HFA-134a.
	19. Subject has a condition or is in a situation that, in the investigator's opinion, may put the subject at significant risk, may confound the study results, or may interfere significantly with the subject's participation in the study
	18. Investigator and study centre personnel directly affiliated with this study and/or their immediate families (defined as spouse, significant other, parent, child, or sibling, whether adopted or biologic)
	17. Exposure to any study drug within 30 days (d) prior to Screening
	16. Clinically significant mental illness that may interfere with the conduct of the study (as determined by the investigator at Screening)
	15. Female subjects who are pregnant or lactating
	14. Known hypersensitivity to DPPC, CP, or hydrofluoroalkane 134a (HFA-134a)
	13. Use of oral analgesics < 2 h prior to Screening or Baseline (oral analgesics > 2 h are permitted as long as ear pain criteria are met per Inclusion Criteria)
	 12. Use of medications with known vasoconstrictive properties (eg, decongestants [Afrin[®], Sudafed[®]]) currently or within 2 h prior to Screening
	11. Seborrheic dermatitis involving the affected external ear canal or pinna
	10. Subjects with erythema of the TM without other evidence of OM

	 AEs recorded over 60 min post dose and at Day 7 for intranasal OP0201 20 mg or placebo
	• Change from Baseline in vital signs (oral temperature, respiratory rate, pulse, and blood pressure) at 60 min post dose for intranasal OP0201 20 mg or placebo
	• Change from Baseline in ENT examination (otoscopy of the ear, nose, and oropharynx) findings at 60 min post dose for intranasal OP0201 20 mg or placebo
	• Change from Baseline in the appearance of the TM (contour, color, fluid, and translucency) at 60 min post dose for intranasal OP0201 20 mg or placebo as measured by otoscopy
Efficacy Endpoints	Exploratory endpoints
	• Responder analysis of ear pain scores at 10, 20, 30, and 60 min post dose for intranasal OP0201 20 mg or placebo using the VAS and the NRS-11
	• Change from Baseline in the VAS and the NRS-11 at 10, 20, 30, and 60 min post dose for intranasal OP0201 20 mg or placebo

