3.4.7.2 Prior and Concomitant Treatments

Prior treatments, defined as those taken within 2 wk before Screening, should be recorded in the eCRF as prior medications. Concomitant treatments, defined as treatments taken after the first dose of study drug, should be recorded in the eCRF as concomitant medications. Concomitant medications will be coded using the latest version of the World Health Organization Drug Dictionary.

Use of medications with known vasoconstrictive properties (eg, decongestants [Afrin[®], Sudafed[®]]) currently or within 2 h prior to Screening are not permitted.

Any medication or therapy that is taken by or administered to the subject during the course of the study must be recorded in the eCRF. The entry must include the dose, regimen, route, indication, and dates of use. The following medications are prohibited until the end of the treatment period on Day 1 (ie, 60 min post dose):

- Medications with known vasoconstrictive properties (eg, decongestants [Afrin[®], Sudafed[®]])
- Oral analgesics

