4 ADVERSE EVENT REPORTING

Throughout the course of the study, all AEs will be monitored and recorded on an AE eCRF, including the AE's description, start and end date, seriousness, severity, action taken, and relationship to the study drug. If AEs occur, the first concern will be the safety of the subjects. All AEs will be followed until resolved or stable and the outcome documented on the eCRF.

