11. SAFETY PARAMETERS

Safety parameters will be listed for the Randomized Population and summarized for the Safety Population unless otherwise noted.

11.1 **AEs**

AEs reported from time of first dose through EOS will be coded according to MedDRA® version 21.1 or later. Each reported AE will be mapped to a PT and SOC. Aside from parameters collected on the eCRF, listings will include date and time of study treatment dosing, MedDRA PT and SOC, Study Day, whether or not the AE is ongoing, AE duration, and whether or not the AE resulted in study discontinuation. For AEs that are ongoing, AE end date will be imputed with subject-level EOS date for the duration calculation.

A treatment-emergent AE (TEAE) will be defined as an AE that began or worsened during or after study treatment dosing on Day 1 and no later than on Day 2. AEs with insufficient date or time information to determine whether or not they were treatment-emergent will be considered treatment-emergent. AEs that began or worsened in severity from Day 3 through EOS will be defined as non-treatment-emergent. AEs that began or worsened in severity before first dose will be recorded as medical history.

All TEAEs will be listed. In addition, separate listings will be done for:

- Treatment-emergent SAEs (TESAEs), to include seriousness criteria
- TEAEs that resulted in study treatment interruption or dose reduction

Confidential Page 16 of 33

- TEAEs that results in discontinuation from the study or study treatment (excluding deaths)
- TEAEs that resulted in death
- Non-treatment-emergent AEs

Listings will be done for the Safety Population.

Incidence of all TEAEs will be summarized by SOC and PTs within SOCs, sorted alphabetically by SOC and PT within SOC unless otherwise noted. In addition, separate summaries will be done for:

- TEAEs assessed as related to study treatment
- TEAEs by maximum severity, with both SOCs and PTs within SOCs sorted by descending incidence among all Study Participants combined
- TESAEs
- TESAEs assessed as related to study treatment

In summaries by relationship to study treatment and maximum severity, missing relationship will be considered related and missing severity will be considered severe. Only the most related TEAE per subject for a given PT will be counted in summaries by relationship; similarly, only the most severe TEAE will be counted in summaries by severity.

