APPENDIX B: TABLES OF CONTENTS FOR TABLES, FIGURES, AND LISTINGS

TABLES

| NUMBER | TITLE | POPULATION | | |
|------------------|--|--------------------------------|--|--|
| Study Population | | | | |
| 14.1.1 | Study Participant Disposition | Randomized | | |
| 14.1.2 | Eligibility | Randomized | | |
| 14.1.3 | Reasons for Screen Failure | Screening excluding Randomized | | |
| 14.1.4 | Protocol Deviations | Randomized | | |
| 14.1.5 | Analysis Populations | Randomized | | |
| 14.1.6 | Demographic and Baseline Characteristics | Safety | | |
| 14.1.7 | Physical Examination | Randomized | | |
| 14.1.8 | Prior Medications | Randomized | | |
| 14.1.9 | Study Treatment Exposure | Safety | | |
| Explorator | y Endpoints | | | |
| = | VAS Observed Values and Changes from Baseline (PID) | Safety | | |
| 14.2.1.1.2 | NRS-11 Observed Values and Changes from Baseline (PID) | Safety | | |
| 14.2.1.2.1 | SPID, VAS | Safety | | |
| 14.2.1.2.2 | SPID, NRS-11 | Safety | | |
| 14.2.1.3.1 | Presence of Any Pain, VAS | Safety | | |
| 14.2.1.3.2 | Presence of Any Pain, NRS-11 | Safety | | |
| 14.2.1.4.1 | Improvement, VAS | Safety | | |
| 14.2.1.4.2 | Improvement, NRS-11 | Safety | | |
| 14.2.1.5.1 | Time to Pain Relief, VAS | Safety | | |
| 14.2.1.5.2 | Time to Pain Relief, NRS-11 | Safety | | |
| 14.2.1.6.1 | Response, VAS | Safety | | |
| 14.2.1.6.2 | Response, NRS-11 | Safety | | |
| 14.2.2.1.1 | PGIC, Summary Statistics for Observed Values | Safety | | |
| 14.2.2.1.2 | PGIC, Frequency Distributions of Observed Values and Response | Safety | | |
| 14.2.2.2.1 | CGI-I, Summary Statistics for Observed Values | Safety | | |
| 14.2.2.2.2 | CGI-I, Frequency Distributions of Observed Values and Response | Safety | | |
| 14.2.3 | AOM Symptoms | Safety | | |
| 14.2.4 | Blinding Index, Study Participants and Physician Investigators | Safety | | |
| Safety End | points | | | |
| 14.3.1.1 | Summary of TEAE Incidence | Safety | | |
| 14.3.1.2.1 | Incidence of TEAEs by System Organ Class (SOC) and Preferred Term (PT) | Safety | | |
| 14.3.1.2.2 | Incidence of TEAEs Related to Study Treatment by SOC and PT | Safety | | |
| 14.3.1.2.3 | Incidence of TEAEs by SOC, PT, and Maximum Severity | Safety | | |
| 14.3.1.2.4 | TEAEs by PT in Descending Order of Incidence | Safety | | |
| 14.3.1.3.1 | Incidence of TESAEs by SOC and PT | Safety | | |
| 14.3.1.3.2 | Incidence of TESAEs Related to Study Treatment by SOC and PT | Safety | | |

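### No planned AE table matches either period named in the primary AE endpoint: the first 60 minutes after dosing, or the record up to Day 7

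*SAP*

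**What the plan says.** The protocol synopsis lists among its primary endpoints "AEs recorded over 60 min post dose and at Day 7 for intranasal OP0201 20 mg or placebo". SAP 4.2.1 keeps both periods and names the attributes to be reported, ending with "relatedness to study treatment of adverse events (AEs) recorded over 60 minutes post dose and at Day 7". SAP section 15 records that expansion as a change from the protocol.

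SAP 11.1 defines a treatment-emergent AE (TEAE) as "an AE that began or worsened during or after study treatment dosing on Day 1 and no later than on Day 2", and states that "AEs that began or worsened in severity from Day 3 through EOS will be defined as non-treatment-emergent". Tables 14.3.1.1 to 14.3.1.4 in SAP Appendix B follow these two groups. An example is Table 14.3.1.2.1, "Incidence of TEAEs by System Organ Class (SOC) and Preferred Term (PT").

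Two protocol passages bear on what happens around the 60-minute mark. Section 3.4.7.2 introduces vasoconstrictive medicines and oral analgesics with the words "The following medications are prohibited until the end of the treatment period on Day 1 (ie, 60 min post dose"). Section 4 gives the content of the AE record as the description, "start and end date, seriousness, severity, action taken" and relationship to study drug. It names no clock time of onset.

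**The concern.** Safety is the only primary objective (Protocol 2.1), and Protocol 1.1.2 says that OP0201 had not been studied in humans before. The first hour is the best-observed part of the trial. The subject is at the centre, AEs are checked at 10, 20, 30 and 60 minutes (Protocol 3.5.2.2), and two classes of medicine that could cause or mask symptoms are barred. After that the subject goes home, the restriction ends, and the one planned AE contact is the follow-up call (Protocol 3.5.2.3). Later AEs depend more on recall, and may reflect other medicines or the illness itself.

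The endpoint names that hour, yet the planned tables merge it with the rest of Days 1 and 2. The endpoint also names Day 7, yet the tables stop one group at Day 2 and start another at Day 3. A reader of the tables could not state the primary AE endpoint for either named period.

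**Working it through.** There is no power calculation or AE rate in the plan to reproduce. The only design figure is 12 per arm, and 2 × 12 = 24 agrees with Protocol 5.2.1.

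**1. Endpoint against tables**

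| Item | Period covered |
|---|---|
| Primary AE endpoint (protocol synopsis; SAP 4.2.1) | 60 minutes post dose, and Day 7 |
| Tables 14.3.1.1 to 14.3.1.3.3 (SAP 11.1, Appendix B) | Dosing to the end of Day 2 |
| Table 14.3.1.4 | Day 3 to end of study |
| Vital signs, ENT and otoscopy tables (SAP 11.2 to 11.4) | Baseline and 60 minutes |

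The other three primary endpoints are tabulated at the time they name. The AE endpoint is not.

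**2. The Day 7 figure cannot be had by adding tables.** A subject with AEs in both windows appears in both. If *a* of 12 subjects in an arm have a TEAE and *b* of 12 have an AE from Day 3 on, the number with any AE lies between max(*a*, *b*) and min(12, *a* + *b*). With assumed counts *a* = 3 and *b* = 2, that is 3 to 5 subjects, or 25.0% to 41.7%. SAP 11.1 also describes its severity, relatedness and seriousness summaries for TEAEs only, not for Table 14.3.1.4.

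**3. How much else shares the window with the first hour.** From dosing at clock hour *h* to the end of calendar Day 2 is 48 − *h* hours. The clock times are assumed:
- *h* = 8: 40 hours, and 1/40 = 2.5%.
- *h* = 18: 30 hours, and 1/30 = 3.3%.

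**4. What pooling does to the any-TEAE row.** One subject is 1/12 = 8.3 points. Assume acute reactions in 2/12 v 0/12, and later Day 1–2 AEs in 1 to 4 other subjects in each arm:

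| Later AEs per arm | OP0201 | Placebo | Difference |
|---|---|---|---|
| 0 | 2/12 (16.7%) | 0/12 (0%) | 16.7 points |
| 1 | 3/12 (25.0%) | 1/12 (8.3%) | 16.7 points |
| 4 | 6/12 (50.0%) | 4/12 (33.3%) | 16.7 points |

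The absolute difference does not move. What changes is the display: a pattern confined to one arm becomes 50% v 33%, with nothing to show that the excess arose within the hour.

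**5. Sensitivity to overlap.** If later AEs occur independently at rate *r* in both arms and can fall on subjects who have already reacted, the any-TEAE difference becomes the first-hour difference × (1 − *r*). With assumed first-hour rates of 40% v 10% (30 points) and *r* = 10%, 20% or 30%, it is 27, 24 or 21 points. None of these rates comes from the documents, and the calculation applies to the any-TEAE row alone.

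**The case against.** The strongest reply is that the endpoint names recording occasions rather than analysis periods. AEs are collected at the Day 1 checks and again at the call, and Protocol 3.5.5 describes one continuous record from dosing to the call. That reading is fair, and neither document promises a comparison by period. It does not remove the mismatch, because the tables follow neither occasion: they cut at the end of Day 2.

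Second, a reader might infer that first-hour AEs go unreported. They do not. Every AE starting in that hour meets the SAP definition of a TEAE and is tabulated by term, severity, relatedness and seriousness. Only the time split is missing. A local spray reaction would also appear under its own preferred term, and in Table 14.3.1.2.2 if judged related. This part of the objection stands, and it limits the consequence.

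Third, with about 24 subjects the listings may be enough. SAP 11.1 puts dosing date and time in the AE listings along with the eCRF fields, so first-hour AEs could be picked out by hand if onset time is recorded. That helps, but a hand count from a listing is not a planned summary of a primary endpoint.

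Fourth, SAP 8.2 says that tables will be presented by time point where appropriate. Neither SAP 11.1 nor Appendix B applies this to AEs. The only post-dose Day 1 window that SAP 8.7 gives for assessments other than the pain scales and PGIC is 45 to 75 minutes, which does not cover the first hour.

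**Conclusion.** The mismatch holds: followed as written, the tables do not yield the primary AE endpoint for the first 60 minutes or cumulatively to Day 7. The effect is on the clarity of safety reporting. The any-TEAE row and the timing information are affected, while the term-level and related-event tables partly preserve an acute signal.

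Two stronger conclusions are tempting, and the documents support neither.
- **That pooling loses the contrast between arms.** In the example with separate subjects the difference stays at 2/12, or 16.7 points. It shrinks only under further assumptions about overlap. SAP 11.1 specifies no AE test, so no loss of power should be claimed.
- **That onset time is not collected.** The protocol's field list names dates only, but it is not an eCRF specification, the eCRF is not among the documents, and SAP 11.1 refers to both date and time when it deals with incomplete AE records.

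The textual finding needs no assumption. The 2.5% to 3.3% share rests on assumed dosing times, and the counts and rates in the examples are illustrative. The Day 2 limit also differs from the open-ended TEAE definition in Protocol 4.1.1, and SAP section 15 does not list that change. That is a separate matter, and this point does not depend on it.

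**What to change.** In Tables 14.3.1.1 and 14.3.1.2.1 add two sets of columns by arm: AEs with onset from dosing to the 60-minute assessment, and all AEs cumulatively to the Day 7 call. Show seriousness, severity and relatedness for both. Table 14.3.1.1 already has rows for related, serious, moderate and severe events, so there the new columns need no new rows.

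Confirm that the eCRF captures onset time for Day 1 AEs. SAP 9.2 speaks of enrolment in the past tense, so a new field may come too late. If times are missing, assign each event by the scheduled AE check at which it was recorded: 10, 20, 30 or 60 minutes, or the follow-up call (Protocol 3.5.2.2 and 3.5.2.3). State in a footnote which rule was used.

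The cost is a few table columns and a short derivation, with no extra subjects, visits or procedures.
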